4. STUDY POPULATION

4.1. Inclusion Criteria

Subjects must satisfy all of the following criteria to be included in the study:

1. Male or female pediatric subjects between birth (defined as 38 weeks gestational age) and less than 18 years of age at the time of consent.
2. Pediatric subjects with the presence of documented VTE confirmed by appropriate diagnostic imaging and requiring anticoagulant therapy for at least 90 days (list of VTE provided in Section [7.1](#)).
-Subjects <6 months old (Cohort 5) with the presence of documented VTE confirmed by appropriate diagnostic imaging and requiring anticoagulant therapy for at least 6 to 12 weeks.
3. Subjects must have received at least 5 days of heparin (LMWH or SP Xa inhibitors or UFH according to the edoxaban label for VTE treatment) therapy prior to randomization to treat the newly identified index VTE. In addition, prior to being randomized to edoxaban or SOC, subjects initially treated with VKA are recommended to have an INR ≤ 2.5 .
4. Subject and/or parent(s)/legal guardian(s) or legally acceptable representative is informed and provides signed consent for the child to participate in the study with edoxaban treatment. Pediatric subjects with appropriate intellectual maturity will be required to sign an assent form in addition to the signed informed consent from the parent(s)/legal guardian(s) or any legally acceptable representative.
5. Female subjects who have menarche must test negative for pregnancy at Screening and must consent to avoid becoming pregnant by using an approved contraception method throughout the study Appendix [17.3](#).

4.2. Exclusion Criteria

Subjects who meet any of the following criteria will be disqualified from entering the study:

1. Subjects with active bleeding or high risk of bleeding contraindicating treatment with LMWH, SP Xa inhibitors, VKAs, or direct oral anticoagulants (DOACs; identified high risk of bleeding during prior experimental administration of DOACs).
2. Subjects who have been or are being treated with thrombolytic agents, thrombectomy or insertion of a caval filter for the newly identified index VTE.
3. Administration of antiplatelet therapy is contraindicated in both arms except for low dose aspirin defined as 1-5 mg/kg/day with maximum of 100 mg/day (see Appendix [17.4.1](#)).
4. Administration of rifampin is prohibited during the study and subjects on concomitant use of rifampin are excluded.
5. a) Subjects with severe hepatic impairment or hepatic disease associated with coagulopathy (eg, acute hepatitis, chronic active hepatitis, and cirrhosis).

- b) Subjects with ALT $>5 \times$ the upper limit of normal (ULN) or total bilirubin $>2 \times$ ULN with direct bilirubin $>20\%$ of the total at Screening.
- c) Subjects with aPTT >50 seconds or international normalized ratio [INR] >2.0 not related to anticoagulation therapy).
- 6. Subjects with estimated glomerular filtration rate (eGFR) $<30\%$ of normal for age and size (see Appendix 17.7).
- 7. Subjects with stage 2 hypertension defined as blood pressure (BP) systolic and/or diastolic confirmed $>99^{\text{th}}$ percentile + 5 mmHg (see Appendix 17.8).
- 8. Subject with thrombocytopenia $<50 \times 10^9/\text{L}$ at Screening Visit. Subjects with a history of heparin-induced thrombocytopenia may be enrolled in the study at the Investigator's discretion.
- 9. Life expectancy less than the expected study treatment duration (3 months).
- 10. Subjects who are known to be pregnant or breastfeeding.
- 11. Subjects with any condition that, as judged by the Investigator, would place the subject at increased risk of harm if he/she participated in the study including contraindicated medications identified in Appendix 17.4.
- 12. Subjects who participated in another interventional clinical study or were treated with an experimental therapy with less than a 30 day wash-out period prior to identifying the qualifying index VTE.
- 13. Hypersensitivity to the active ingredient or to any of the excipients of any components of the trial treatment.
- 14. Patients with a history of thrombosis who are diagnosed with antiphospholipid syndrome who are triple positive (for lupus anticoagulant, anticardiolipin antibodies, and anti-beta 2-glycoprotein I antibodies).

4.3. Additional Requirements

4.3.1. Stopping Rules for Age-based cohort during PK/PD assessment:

- In each age cohort if the estimated edoxaban median AUC based on the observed PK data in the approximately 12 subjects (between 5 and 12 subjects in Cohort 5) on Day 5 PK assessment is 50% higher or 50% lower than the median AUC from the simulated patient population profiles, dose reevaluations for Phase 3 subjects will be recommended to achieve the exposure comparable to adult 60 mg doses. The enrollment of subjects in the corresponding age cohort will be put on hold until reevaluation of the dose for this age cohort.

4.3.2. Stopping Rules for Study:

An IDMC may recommend termination of the study. Termination may be made for any of the following reasons:

- Concern about significantly higher bleeding risk relative to one of the study arms,
- Concern about drug-induced liver injury,
- Any other safety concern based on benefit/risk evaluation.

5. STUDY TREATMENT(S)

5.1. Assigning Subjects to Treatments and Blinding

5.1.1. Treatment Group(s)

All subjects will be assessed for eligibility in the study in accordance with the inclusion/exclusion criteria after VTE diagnosis. Eligible subjects will be stratified by age and region (ie, US/Canada, Europe, Asia/Pacific, and Rest of the World), and then randomized in a 1:1 ratio to the edoxaban treatment arm or the SOC treatment arm, respectively.

Study treatment should be administered on the same day as randomization (Day 1). Subjects randomized to edoxaban and previously treated with VKA, can initiate edoxaban treatment only after the INR is ≤ 2.5 ; or 12 hours after last dose of LMWH.

The Day 5 PK/PD assessment will be adjusted accordingly to have 5 doses of edoxaban prior to assessment. For subjects participating in PK/PD assessment and receiving LMWH twice a day and who already received a morning dose on Day 1 prior to randomization, edoxaban can be started on the morning of Day 2 (12 hours \pm 3 hours after last evening dose of LMWH).

Initial treatment with heparin (with overlapping VKAs if needed) for index VTE prior to randomization must be within the range of at least 5 - 15 days and up to 20 days with Sponsor approval. In addition, prior to being randomized to edoxaban or SOC, subjects initially treated with VKA should have an INR ≤ 2.5 .

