5.2.4.1. Instruct the subject to begin taking edoxaban

LMWH / SP Xa inhibitors / UFH (with overlapping VKAs if needed) treatment during Pre-randomization must be discontinued at Randomization day (Day 1). Edoxaban dosing should begin when INR is ≤ 2.5 for warfarin-treated subjects. For subjects participating in PK/PD assessment and receiving LMWH twice a day and who already received morning dose on Day 1 prior to randomization, edoxaban can be started on the morning of Day 2 (12 hours \pm 3 hours after last evening dose of LMWH).

1. A subject who was on LMWH twice a day regimen will start edoxaban dosing 12 \pm 3 hours after the last LMWH dose
2. A subject who was LMWH QD regimen or on SP Xa inhibitors (once daily) will start edoxaban dosing 24 \pm 3 hours after the last LMWH or SP Xa inhibitor dose
3. A subject who was on an UFH regimen will start edoxaban dosing 4 \pm 1 hour after the last UFH dose
4. A subject who had received VKA during the Screening period, VKA should be stopped 24 hours prior to randomization (INR should be ≤ 2.5 in the absence of VKA therapeutic effect). Subject can take edoxaban on the day of randomization.

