6.3. Main Treatment Period

The Main Treatment Period is defined as the time from randomization until the end of Month 3 of treatment. The Main Treatment Period for subjects <6 months old (Cohort 5) is defined as the time from randomization until the end of anticoagulant therapy for at least 6 to 12 weeks.

6.3.1. Subjects randomized to the edoxaban treatment arm:

For the approximately first 12 subjects of each age cohort randomized in edoxaban-treatment arm, two blood samples will be collected on Day 5+3 days. Dosing on Day 5 will be done in the study center. Note: If the subject did not initiate dosing of edoxaban on the randomization day (Day 1), the Day 5 PK/PD assessment should be scheduled when the actual Day 5 dose is taken.

Edoxaban will be started orally at the age/weight/renal function appropriate dose (depending on the results of the ongoing U157 study) for the treatment period. The study will start enrollment from older to younger children as data from the single dose PK, PD study become available for each age cohort (Study U157). After Month 3, dispense may be provided for a 3-month period to align with the visit schedule based on approval of the Sponsor.

For subjects in Cohort 5, the Principal Investigator (PI) may use medical discretion and clinical judgment to determine the duration of anticoagulation treatment. For these subjects, the intended duration of treatment should be at least 6 to 12 weeks. If 6 weeks' duration is chosen, a radiologic VTE image will be taken and will be assessed by the PI to determine if an additional 6 weeks of treatment is required. After 12 weeks, an additional radiologic VTE image will be taken by the PI to assess whether the subject should continue on treatment into the extension.

Approximately 12 subjects from each age cohort (total of approximately 53 to 60 subjects) will participate in the multiple-dose PK/PD assessment (subject number is determined by evaluable blood specimens demonstrating edoxaban exposure). For the youngest Cohort 5 (birth to <6 months), 5 to 12 subjects on edoxaban will be enrolled.

- Ages 12 to <18 years (N≈12)
- Ages 6 to <12 years (N≈12)
- Ages 2 to <6 years (N≈12)
- Ages 6 months to <2 years (N≈12)
- Ages birth to <6 months (N≈5-12)

6.3.1.1. Study Day 5 (+3 days) for Subjects Randomized to Edoxaban Only (Visit 2a)

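### Section 5.1.1 allows edoxaban 12 hours after LMWH without naming a regimen; read alone, that is 9 hours before the earliest start Section 5.2.4.1 sets after once-daily LMWH

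*Combined protocol and SAP*

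**What the plan says.** Section 5.1.1 first asks that study treatment be given on the day of randomization. It then says that edoxaban-arm subjects previously treated with VKA "can initiate edoxaban treatment only after the INR is" ≤ 2.5, and after a semicolon adds "or 12 hours after last dose of LMWH". No LMWH regimen is named in that sentence. The only regimen named in Section 5.1.1 is in the next paragraph, which has a narrower scope: "For subjects participating in PK/PD assessment and receiving LMWH twice a day and who already received a morning dose on Day 1". There the interval is 12 ± 3 h. The section closes with a further INR statement: "subjects initially treated with VKA should have an INR" ≤ 2.5 before randomization.

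Section 5.2.4.1, which tells sites how to start edoxaban, gives a list by prior regimen:

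- "A subject who was on LMWH twice a day regimen will start edoxaban dosing 12" ± 3 hours after the last LMWH dose.
- "A subject who was LMWH QD regimen or on SP Xa inhibitors (once daily) will start edoxaban dosing 24" ± 3 hours after the last dose.
- After UFH, 4 ± 1 hours.
- After VKA, stop the VKA 24 hours before randomization, with INR ≤ 2.5.

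The same section also says, of warfarin-treated subjects, "Edoxaban dosing should begin when INR is" ≤ 2.5.

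The synopsis refers to Section 5.2.4.1 where it describes starting edoxaban. For a subject on VKA randomized with INR ≥ 2.5, it makes the delay of edoxaban optional.

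**The concern.** Two current sections give a first-dose time after LMWH, and they agree for only one of the two LMWH regimens that the protocol foresees. A child given once-daily LMWH on the morning of Day 1 could, under Section 5.1.1 alone, receive edoxaban that evening. Under Section 5.2.4.1 the dose is not due until about the next morning. The evening dose would fall halfway through the LMWH interval, with two anticoagulants acting together.

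Once-daily LMWH is not hypothetical. Section 5.2.4.1 lists it, and Section 5.2.4.2 mentions once-daily therapeutic enoxaparin. The synopsis leaves pre-randomization treatment to the investigator or the diagnosing clinic. Against that, the protocol's own enoxaparin treatment doses are twice daily (Section 5.1.1.2 and Table 17.2), so once-daily use may be uncommon.

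What is at stake is avoidable bleeding risk in the hours after the switch. On-treatment bleeding is counted from the first dose of study drug (Section 11.4.3.1), so a bleed during the overlap would be counted as on-treatment in the edoxaban arm.

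**Working it through.** The check is interval arithmetic on the stated times, in hours after the last dose of the earlier drug.

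**Inputs**

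- Section 5.1.1, LMWH with no regimen named: 12 h, read as an earliest time.
- Section 5.2.4.1, twice-daily LMWH: 12 ± 3 h.
- Section 5.2.4.1, once-daily LMWH or SP Xa inhibitor: 24 ± 3 h.

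**Windows in Section 5.2.4.1**

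- Twice daily: 12 − 3 = 9 h to 12 + 3 = 15 h.
- Once daily: 24 − 3 = 21 h to 24 + 3 = 27 h.

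**The 12 h time against each window**

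| Prior LMWH | Window in 5.2.4.1 | Is 12 h inside? | Gap |
|---|---|---|---|
| Twice daily | 9 to 15 h | Yes, at the centre | None to the target |
| Once daily | 21 to 27 h | No | 21 − 12 = 9 h before the earliest time; 24 − 12 = 12 h before the target |

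For twice-daily LMWH the two sections share the 12 h target. Section 5.1.1 only leaves out the tolerance: taken strictly as an earliest time, it removes 12 − 9 = 3 h of the 15 − 9 = 6 h window, which errs on the cautious side. For once-daily LMWH the error runs the other way.

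**Can both sections be obeyed?** Yes. A first dose at 21 to 27 h is later than 12 h, so it meets both. The same-day request in Section 5.1.1 is not absolute: Section 6.2 and footnote a of Table 17.1 let randomization fall on the day before dosing, and Section 6.3.1 provides for a first dose after Day 1. The fault is that Section 5.1.1 also allows times from 12 h up to 21 h, which Section 5.2.4.1 excludes.

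**INR wording.** Section 5.1.1 makes INR ≤ 2.5 a condition for starting. The synopsis makes delay optional at INR ≥ 2.5, and its trigger (≥ 2.5) and release (≤ 2.5) overlap at exactly 2.5.

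No subject count can be worked out, because the documents give no share of children on once-daily LMWH before randomization.

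**The case against.** The strongest reply is that Section 5.2.4.1 already settles the matter. It is the dedicated starting instruction, it covers every prior regimen in mandatory wording, and the synopsis sends the reader there. Section 5.1.1 sits under treatment assignment, gives no interval for UFH or SP Xa inhibitors, and cannot be used as a complete switching guide. Its sentence opens with VKA-treated subjects and is worded as a restriction. A careful site would follow Section 5.2.4.1 and dose correctly.

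Most of this stands, and it keeps the severity low. It does not remove the inconsistency. Section 5.1.1 neither points to Section 5.2.4.1 nor limits its 12 h to twice-daily LMWH. The synopsis reference is not a statement of precedence. Reading the sentence as confined to VKA-treated subjects still leaves the LMWH regimen unnamed.

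Two stronger readings are tempting, and the documents do not support either:

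- A reader might infer that the protocol requires early dosing after once-daily LMWH, or that the two sections cannot both be followed. They can, as the working shows.
- A reader might infer from the semicolon and the word 'or' that a VKA-treated child with a high INR may start simply because 12 h have passed since LMWH. The closing sentence of Section 5.1.1 and the INR statements in Section 5.2.4.1 largely rule this out. What remains is loose wording.

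**Conclusion.** The point holds as a minor, safety-relevant inconsistency. The 12 h clause in Section 5.1.1 is wrong as written for once-daily LMWH: read alone, it allows edoxaban 9 h before the earliest time in Section 5.2.4.1 and 12 h before the target. It is right for twice-daily LMWH apart from the missing tolerance.

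This rests on reading the 12 h as an earliest time that applies to any LMWH regimen, which the sentence's wording allows. Actual harm would need both a child on once-daily LMWH and a site that relied on Section 5.1.1 without consulting Section 5.2.4.1. How often that would happen is unknown, and it may be rare.

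A reader might also look for damage to the analysis, and there is none in the primary one. Time to first efficacy event runs from randomization (Section 11.4.1.1), the Day 5 PK/PD visit follows the fifth edoxaban dose whenever dosing starts, and no sample-size, power or alpha figure depends on this interval.

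**What to change.** Replace the INR and LMWH clause in Section 5.1.1 with text such as:

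> *Edoxaban is started according to the prior-regimen intervals and VKA stopping rule in Section 5.2.4.1. In subjects previously treated with VKA it is started only once INR is ≤ 2.5. If INR is still > 2.5 when the interval has elapsed, the first dose is given as soon as INR is ≤ 2.5.*

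The last sentence is needed because the windows close at 15 h (twice daily) and 27 h (once daily). If the text simply required both the window and the INR, a child whose INR fell later could never meet both conditions. Referring to Section 5.2.4.1, and not repeating its figures, keeps one source for the intervals.

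As a separate consistency edit, change the synopsis so that edoxaban *must* be delayed when INR is *> 2.5*, in place of the optional delay at ≥ 2.5. This matches the condition in Section 5.1.1 and removes the overlap at exactly 2.5.

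The cost is a few sentences in Section 5.1.1 and one wording change in the synopsis, made as a protocol clarification. Design, sample size and analysis stay as they are.

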5.1.1.1. Edoxaban Treatment Arm

Edoxaban treatment will be dispensed to the subject on a monthly visit schedule. After Month 3 the distribution of edoxaban may be for a 3-month period to align with the visit schedule, with the Sponsor's approval. Edoxaban will be started orally at the age/weight/renal function appropriate dose (depending on the results of the ongoing U157 study) for the Treatment Period.

5.1.1.1.1. Edoxaban dose recommended for 12 to <18 years old pediatric subjects

Edoxaban treatment will be dispensed to the subject on a monthly visit schedule (see caveat above). The oldest cohort (12 to <18 years old) will receive tablets (15 and/or 30 mg strength, see [Table 5.1](#)). (Doses for all subsequent age cohorts will be by notification to the investigative sites.) Subjects will be instructed to take edoxaban (tablets) orally once a day, at the same time every day, with or without food. Tablets should be swallowed with a glass of water.

Only on Day 5 (+3), the approximately first 12 subjects participating in PK/PD assessment should be fasting one hour prior to intake of edoxaban dose and a maximum of 2 hours after taking edoxaban dose.

Table 5.1: Edoxaban Dose Recommended For All 5 Cohorts (12 to <18 years, 6 to <12 years, 2 to <6 years, 6 months to <2 years, and birth to <6 months)

Age	Body Weight	Dose (Tablet)	Dose (Suspension) (6 mg/mL concentration) ^{c,e}	Dose Reduction ^a
12 to <18 years ^b (At date of consent)	≥60 kg	60 mg QD	NA	45 mg QD
	≥30 and <60 kg	45 mg QD	NA	30 mg QD
	<5th Percentile for Age ^c	30 mg QD	NA	NA
6 to <12 years (At date of consent)	<60 kg Dosed based on mg/kg ^d	NA	1.2 mg/kg with a maximum dose of 45 mg	0.8 mg/kg, with a maximum dose of 45 mg
2 to <6 years (At date of consent)	Dosed based on mg/kg	NA	1.4 mg/kg with a maximum dose of 45 mg	0.7 mg/kg, with a maximum dose of 24 mg
6 months to <2 years (At date of consent)	Dosed based on mg/kg	NA	1.5 mg/kg with a maximum dose of 45 mg	0.75 mg/kg with a maximum dose of 24 mg
>28 days to <6 months (At date of consent)	Dosed based on mg/kg	NA	0.8 mg/kg with a maximum dose of 12 mg/kg	0.4 mg/kg, with a maximum dose of 6 mg/kg
38 weeks gestation to ≤28 days (At date of consent)	Dosed based on mg/kg	NA	To be determined by the IDMC	0.4 ^f mg/kg, with a maximum dose of 6 mg/kg

Abbreviations: eGFR = estimated glomerular filtration rate; IDMC = Independent Data Monitoring Committee; NA = not applicable; P-gp = P-glycoprotein; QD = once a day

^a Conditions for dose reduction:

If a subject requires concomitant administration of P-gp inhibitor (Appendix 17.4.6), the edoxaban dose will be reduced during P-gp administration and re-established to the original dose once P-gp inhibitor administration had concluded.

Edoxaban dosage regimen will be reduced permanently for subjects with moderate renal impairment for the subject's age and size at randomization as determined by the age appropriate formula: Cockcroft-Gault equation for pediatric subjects ≥12 years of age and modified Schwartz equation for pediatric subjects <12 years of age). Refer to Appendix 17.7 for eGFR values below which dose reduction should be implemented.

If a subject experiences a change in renal function from normal to eGFR ≥30% to ≤50% after randomization, the measurement will be repeated within 1 week to 10 days after correction of the underlying factor's causing pre-azotemia. If the repeat measurement confirms the reduced eGFR, the edoxaban dose reduction will be permanent even if the subject experiences an improvement in the eGFR during the course of the study.

^b Dose reduction due to body weight applies only for fixed doses in subjects 12 to <18 years of age:

If body weight increases or decreases from the categories of weight defined at consent, the subject will be dose adjusted. Subjects who are ≥60 kg of body weight at consent and drop below that body weight will receive 45 mg dose at any subsequent visit. Subjects who are ≥30 and <60 kg at consent and increase their weight to ≥60 kg will increase their dose to 60 mg.

^c Edoxaban dosage regimen will be reduced permanently for subject with body weight <5th percentile for age.
Refer to Appendix 17.9.

^d Edoxaban granulation will be diluted with 8 mL water to provide a concentration of 6 mg/mL dosing suspension. If body weight increases or decreases from the categories of weight defined at consent, the subject will be dose adjusted. Subjects who are \geq 60 kg of body weight at consent and drop below that body weight will receive 45 mg dose at any subsequent visit. Subjects \geq 30 and <60 kg at consent increasing their weight to \geq 60 kg will increase their dose to 60 mg.

Note: Dose is based upon weight at corresponding visit.

^e Edoxaban granules are for subjects <12 years of age only. Subjects 12 to <18 years of age should use crushed edoxaban tablets. For those subjects cannot swallow whole tablets, edoxaban tablets may be crushed and mixed with 2 to 3 ounces of water and immediately administered by mouth or through a gastric tube. The crushed tablets may also be mixed into applesauce and immediately administered..

^f The IDMC may meet and conclude that subjects \leq 28 days old no longer require a dose reduction and may recommend a revised dose based on the availability and re-review of PK data.

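### Table 5.1 gives the reduced edoxaban dose for ages 6 to <12 years the same 45 mg maximum as the full dose, so from 56.25 to <60 kg the required reduction is nil

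*Combined protocol and SAP*

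**What the plan says.** All of this is in the combined protocol and SAP.

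- **The row in question.** In Table 5.1 (Section 5.1.1.1.1), the 6 to <12 years row has the weight entry "<60 kg Dosed based on mg/kg". The full dose is 1.2 mg/kg with a 45 mg maximum. The reduced dose is "0.8 mg/kg, with a maximum dose of 45 mg".
- **When the reduced dose applies.** Footnote a says that, with a P-gp inhibitor, "the edoxaban dose will be reduced during P-gp administration and re-established to the original dose once P-gp inhibitor administration had concluded". For renal function it says "Edoxaban dosage regimen will be reduced permanently for subjects with moderate renal impairment". Sections 5.5 and 17.4.6 repeat the P-gp rule in mandatory terms and exempt amiodarone.
- **Neighbouring rows.** At 2 to <6 years the full dose is 1.4 mg/kg (maximum 45 mg) and the reduced dose is "0.7 mg/kg, with a maximum dose of 24 mg". At 6 months to <2 years the full dose is 1.5 mg/kg (maximum 45 mg) and the reduced dose is "0.75 mg/kg with a maximum dose of 24 mg". Adolescents go from 60 to 45 mg at 60 kg or more, and from 45 to 30 mg at 30 to <60 kg.
- **At 60 kg and above.** Footnote d is marked on the weight entry of the 6 to <12 years row. It says that subjects of at least 30 "and <60 kg at consent increasing their weight to" at least "60 kg will increase their dose to 60 mg". Section 5.1.1.1.2 sets a 45 mg once-daily ceiling for everyone under 12 years. Neither place gives a reduced dose for a child in this cohort who reaches 60 kg.

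**The concern.** A cap on a weight-based dose takes over once the child is heavy enough. If the full and reduced doses share one cap, the full dose stops rising first and the reduced dose then catches up with it. From the weight at which they meet, the instruction to reduce has no effect.

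The protocol treats P-gp inhibition and moderate renal impairment as reasons to give less edoxaban. A child in the affected band who starts clarithromycin, which Section 17.4.6 lists, would continue on an unchanged anticoagulant dose. What is at stake is that child's exposure and risk of major or clinically relevant non-major bleeding, which is a safety endpoint of the trial.

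**Working it through.** The documents give no derivation of the 45 mg reduced-dose maximum, so there is no calculation of the plan's own to reproduce. The check uses only the entries printed in Table 5.1.

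**Step 1. Dose rules** (w = weight in kg, w < 60)

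- Full dose = min(1.2w, 45) mg
- Reduced dose = min(0.8w, 45) mg
- Cut = 1 − reduced/full

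**Step 2. Weights at which the caps take over**

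- Full dose: 45/1.2 = 37.5 kg
- Reduced dose: 45/0.8 = 56.25 kg

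Up to 37.5 kg the cut is 1 − 0.8/1.2 = 33.3%. From 37.5 to 56.25 kg it is 1 − 0.8w/45. From 56.25 kg it is 1 − 45/45 = 0.

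**Step 3. Values, as printed and with a 30 mg reduced-dose cap**

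| Weight (kg) | Full (mg) | Reduced, as printed (mg) | Cut, as printed | Reduced, 30 mg cap (mg) | Cut, 30 mg cap |
|---|---|---|---|---|---|
| 30 | 36 | 24 | 33.3% | 24 | 33.3% |
| 37.5 | 45 | 30 | 33.3% | 30 | 33.3% |
| 40 | 45 | 32 | 28.9% | 30 | 33.3% |
| 45 | 45 | 36 | 20.0% | 30 | 33.3% |
| 50 | 45 | 40 | 11.1% | 30 | 33.3% |
| 55 | 45 | 44 | 2.2% | 30 | 33.3% |
| 57 | 45 | 45 | 0% | 30 | 33.3% |

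At 57 kg, 0.8 × 57 = 45.6 mg, which the cap brings to 45 mg, or 45/57 = 0.79 mg/kg. A 57 kg adolescent on the same 45 mg goes to 30 mg, or 30/57 = 0.53 mg/kg.

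**Step 4. Does the cap move with the dose in other rows?**

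- 2 to <6 years: dose ratio 0.7/1.4 = 0.50; cap ratio 24/45 = 0.53; caps reached at 32.1 and 34.3 kg.
- 6 months to <2 years: dose ratio 0.75/1.5 = 0.50; cap ratio 24/45 = 0.53; caps reached at 30.0 and 32.0 kg.
- 6 to <12 years: dose ratio 0.8/1.2 = 0.67; cap ratio 45/45 = 1.00; caps reached at 37.5 and 56.25 kg.

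The >28 days to <6 months row also halves both figures, but its caps are printed in mg/kg and so could never bind. It is not relied on here.

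**Step 5. Candidate caps**

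- Scaling the full-dose cap by the row's own dose ratio gives 45 × 0.8/1.2 = 30 mg. It is reached at 30/0.8 = 37.5 kg, the same weight as the full-dose cap.
- Borrowing 24 mg from the younger rows would bind at 24/0.8 = 30 kg. The cut would deepen from 1 − 24/36 = 33.3% there to 1 − 24/45 = 46.7% from 37.5 kg.

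**Step 6. At 60 kg and above**

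- Footnote d (full dose 60 mg): a 45 mg reduced cap cuts 25%; a 30 mg cap cuts 50%.
- Section 5.1.1.1.2 (full dose 45 mg): a 45 mg cap cuts 0%; a 30 mg cap cuts 33.3%.

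**The case against.** **No fixed percentage is required.** A reader might infer from the table above that the protocol's rule is broken at every weight over 37.5 kg. The documents do not support that. They require a lower dose and set it at 0.8 mg/kg; they nowhere promise a one-third cut. Nominal cuts across Table 5.1 already differ (25%, 33% and 50%). From 37.5 kg to just under 56.25 kg the child does receive a lower dose, exactly as printed. This objection stands and confines the contradiction to 56.25 to <60 kg.

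**The cell may restate the general ceiling.** Section 5.1.1.1.2 caps everyone under 12 years at 45 mg, and a 57 kg child's full dose is then already 0.79 mg/kg, close to the reduced rate. It follows that nobody can say whether 45 mg was modelled, carried over or mistyped. A reader might infer that 30 mg was intended, but no text says so. The contradiction remains on either reading: 45 mg is also the dose for a child of that weight with neither condition, and footnote a requires less than that.

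**The operative dose may sit elsewhere.** Doses for the younger cohorts reach sites by separate notification after IDMC approval, and Section 5.1.2 has the IXRS take reduction factors into account. Neither is in these documents. One therefore cannot conclude that any child has been under-reduced, only that the protocol's table would allow it.

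**The mandate is mixed.** Section 5.3.1 says a subject may have the dose reduced. The synopsis, footnote a and Sections 5.5 and 17.4.6 are mandatory, and a dose equal to the full dose satisfies neither wording.

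**Footnote d may be misplaced.** Its weight text nearly repeats the adolescent footnote b, and other footnote markers in the table look unreliable. That is a fair reason to treat the 60 kg conflict as secondary. As printed, though, the two rules disagree.

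**Conclusion.** The point holds for a narrow band. From 56.25 to <60 kg, the reduced dose in the 6 to <12 years row equals the full dose of 45 mg, against a stated requirement to reduce. No other section supplies a lower maximum. The narrowing from 37.5 to 56.25 kg is an inconsistency with the adolescent 45-to-30 mg step and with the 45-to-24 mg caps in the next two younger rows; it is not a breach.

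The number of children concerned is not stated and is probably small: edoxaban arm, this age cohort, the heavier weights, and a qualifying inhibitor or moderate renal impairment. The documents give no PK figure for this weight band, so the effect on exposure or bleeding is unknown. The conclusion assumes that sites dose from the table as printed. Since it concerns individual dosing of an anticoagulant in children and is simple to correct, it should be corrected even if few are affected.

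**What to change.** 1. **Lower the reduced-dose maximum in this cell below 45 mg.** The candidate is 30 mg, which keeps the row's 33% cut at every weight below 60 kg and matches the adolescent step. Clinical pharmacology should confirm it against the population PK model first, looking at under-exposure as well as over-exposure, because a 57 kg child would receive 0.53 mg/kg. The IDMC should then approve it.
2. **Check the Cohort 2 dose notification and the IXRS dose rules** for the same 45 mg reduced-dose cap.
3. **Separately, settle the dose at 60 kg and above.** Either keep the 45 mg ceiling of Section 5.1.1.1.2, delete the 60 mg sentence from footnote d and state a 30 mg reduced dose (if that cap is confirmed); or keep 60 mg, add a line for 60 kg or more with 60 mg full and 45 mg reduced as for adolescents, and write the exception into Section 5.1.1.1.2. A 30 mg cap should not be applied to a child on 60 mg, since that would be a 50% cut against 25% for an adolescent.

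**Cost.** One table cell, footnote d and possibly one sentence of Section 5.1.1.1.2. The work lies in the PK confirmation, the IDMC approval, the IXRS check, and an amendment under Section 15.7 (IRB/EC and, where appropriate, regulatory approval) or a site dose notification. Nothing changes in the sample size or the analysis.
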